724 **5.2.1. Principles to be Followed in Primary Analysis**

725 Model assumptions for the ANCOVA will be checked as described in Section 2.1.1,
726 including linearity of baseline refractive error, normal distribution, and equal variance
727 across treatment groups. If baseline refractive error was included as a continuous variable
728 in the analysis from Section 2.1, it will be included as a continuous variable in this model
729 as well; otherwise, it will be categorized.

730
731 There will be no imputation for missing data; however, baseline characteristics of
732 participants with and without follow up will be tabulated at each time point. In the event
733 there is a clinically relevant imbalance between those with and without follow up, a
734 propensity score-weighted analysis will be performed as a sensitivity analysis.

735
736 The primary analysis will follow a modified intention-to-treat principle, with all
737 participants analyzed according to their randomized treatment group. To be included in
738 the analysis, the 24-month visit must be completed no earlier than 630 days (≥ 21
739 months) and no later than 899 days (< 30 months) after randomization. If the 24-month
740 visit is not completed within this analysis window, the 18-month visit data will be used
741 instead (if available and if within 24-month window). The 36-month visit must be
742 completed no earlier than 900 days (≥ 30 months) and no later than 1440 days (≤ 48
743 months) after randomization.

744
745 As a sensitivity analysis, the primary analysis will be repeated but limited to participants
746 who completed each visit within the protocol window of +/- 3 months.

747 A separate sensitivity analysis will repeat the primary analysis but be limited to
748 participants who were not treatment crossovers at any point in the study.

749
750
751
752
753
754
755
756
757
758
759
760
761
762
763
764
765
766
767
768
769
770
771
772
773
774
775
776
777
778
779
780
781
782
783
784
785
786
787
788
789
790
791
792
793
794
795

5.3.Secondary Analysis—Comparison of Axial Length and Other Biometric Measurements Between Treatment Groups at 24 and 36 Months

At the 24-month and 36-month time points, mean axial length measurement, flat corneal radius, anterior chamber depth, and lens thickness (if available) will each be compared between treatment groups using an ANOVA model. Adjustment for baseline is not possible given that these measurements were added late in the study (with Protocol Amendment II) and therefore not collected at baseline. Treatment group differences, 95% confidence intervals, and p-values will be calculated. The type I error rate in this secondary analysis will be controlled using false discovery rate (FDR) to control the FDR at 5% and to adjust the p-values for multiplicity.

Longer axial length is expected to be related to more myopic progression. The other biometric measures may or may not be related to myopic progression. To assess this, Spearman correlation coefficients will be calculated for the relationship between the biometric measures (mean axial length measurement, flat corneal radius, anterior chamber depth, and lens thickness) and refractive error at the 24-month and 36-month time points. Correlation coefficients with an absolute value of 0.60 or higher will be considered strong correlations.

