The parent/guardian of each subject will be compensated \$50 for completion of each of the 24-month and 36-month visits, up to a total of \$100. If there are extenuating circumstances, and the subject is unable to complete the annual study visits without additional funds due to travel costs, additional funds may be provided.

The study will pay for visits specific to the research study, but will not pay for usual care visits that would occur whether or not the subject was in the study. The cost of usual care visits will be the responsibility of the subject or his/her insurance company.

The study will pay for a pair of spectacles (lenses and frames) at the first extension study visit (24 months or 36 months). Spectacle changes / new spectacles prescribed at other times will not be paid for by the study.

Treatment after 18-months is at investigator discretion and is not part of this protocol. Any costs associated with treatment will not be paid for by the study.

Risks

The procedures in this study are part of daily eye care practice in the United States and pose no known risks.

Subject Contact During Follow Up

Between annual visits, subjects may be called periodically by the Jaeb Center to promote retention.

Re-consenting of Subjects

An addendum to the original informed consent form (and addendum to the assent form, if required) for the extension study will be signed by parents who elect to continue their child's study participation. Re-consenting will occur at the next 12, 15, or 18-month randomized trial visit but could occur at other times either before or after participation in the 18-month trial has ended. A subject (and respective parent) may withdraw from the study at any time.

294295 Statistical Analyses

The following analyses will be completed separately at the 24-month and 36-month visits to evaluate the effect of the overminus treatment approach followed by usual clinical care versus the non-overminus treatment approach followed by usual clinical care:

- Spherical equivalent refractive error will be compared between treatment groups using an ANCOVA model that adjusts for baseline spherical equivalent refractive error. The treatment group difference and a 95% confidence interval will be calculated.

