4.3.2 Risk of Overminus Lens Therapy

The risks involved in the study are identical to those for a child treated with overminus lens therapy who is not participating in the study.

Some subjects treated with overminus lenses may experience eye strain when wearing the spectacles; the eye strain typically dissipates with removal of the spectacles.

Among previous retrospective reports, some have indicated that there may be an increased rate of myopia development when accommodation is stimulated, 11,18,31 whereas others have reported no increase in myopia following overminus lens therapy. However, unpublished data from the current ongoing randomized trial suggests that myopic progression over one year is greater in subjects treated with overminus lenses vs. those treated with non-overminus lenses, and that myopic progression was most often observed in overminus group subjects who had spherical equivalent myopia of -0.50 D or greater at baseline (PEDIG unpublished, 2019).

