35 on SE in the least hyperopic eye as follows: 1) full correction for SE myopia, 2)
36 sphere power that resulted in a plano SE lens (with symmetrical reduction in the
37 most hyperopic eye, if needed).

38
39 Note: any mention of refractive error from this point on will refer to refractive error in the
40 most myopic eye at baseline; this is because treatment was prescribed based on this eye
41 and eligibility criteria, so this is the eye that will be used for any analyses involving
42 refractive error.

43
44 **2. Objective I: Effect of Overminus Lenses on Distance Control**

45
46 **2.1 Primary Analysis – Efficacy of Overminus Treatment (12 Months, On-
47 Treatment)**

48 The primary analysis will be a two-sided comparison of mean 12-month control of the
49 distance exodeviation (mean of 3 measurements) between the treatment groups using an
50 analysis of covariance (ANCOVA) model which adjusts for the following baseline
51 factors to account for potential residual confounding: distance control, distance PACT,
52 age, and refractive error (in the most myopic eye at baseline). The ANCOVA model will
53 test the hypothesis that the treatment effect is different from zero (superiority hypothesis)
54 using a type I error rate of 5%. The treatment group difference (overminus – non-
55 overminus) and corresponding 95% confidence interval and p-value will be calculated.
56 While use of ADHD medication was specified in the protocol as a baseline adjustment
57 factor, this information was not collected at baseline due to an oversight. Therefore, this
58 will not be one of the adjustment factors in the model.

59
60 **2.1.1. Principles to be Followed in Primary Analysis**

61 Model assumptions for the ANCOVA will be assessed, including linearity of the
62 adjustment covariates (baseline distance control, distance PACT, age, and refractive
63 error), normal distribution and equal variance across the treatment groups. The linearity
64 assumption of the baseline covariates will be evaluated using descriptive scatterplots and
65 by categorizing each of the baseline factors in the model to check for approximate
66 linearity of the coefficients across ordered categories. A baseline covariate will be
67 included as a continuous variable in the model if the assumptions for linearity are met for
68 that covariate; otherwise, the baseline covariate will be categorized.

69
70
71
72
73
74
75
76
77
78
79
80
81
82
83
84
85
86
87
88
89
90
91
92
93
94
95
96
97
98
99
100
101

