520 control at 18 months. All planned subgroup analyses will repeat the primary analysis
521 (Section 2, excluding the sensitivity analysis). The specific subgroups of interest are:

- 522 • Baseline distance control score by severity (2 to <3, 3 to <4, 4 to <5 points)

- 523 • Baseline age group (3 to <7 years vs. 7 to <11 years)
- 524 • Spherical equivalent refractive error level (-6.00 to -0.50D vs. -0.375 to +1.00D)
- 525 • Accommodative convergence/accommodation (AC/A) ratio (<2.5, 2.5 to 6.0, >6)

526

527 Exploratory analyses performed on the IXT3 pilot study data suggested that overminus
 528 spectacles might be effective for participants with very poor baseline distance control (4-
 529 <5 points), a finding that was somewhat unexpected. We would like to further explore
 530 whether treatment effect varies by baseline control. Because children 7 to < 11 years of
 531 age likely have greater accommodative demands (e.g., schoolwork) than children 3 to < 7
 532 years of age, and because the visual systems of the two groups are at different stages
 533 developmentally, it is possible that their response to overminus lenses might be different.
 534 Since participants with hyperopia and participants with myopia may use their
 535 accommodative system differently, the response to overminus lenses may be different.
 536 We might expect that participants with high AC/A ratios would respond to overminus
 537 spectacles better than participants with lower AC/A ratios given that one of the
 538 mechanisms of action of overminus is to stimulate accommodative convergence, thereby
 539 reducing the angle of exodeviation and allowing fusion. The IXT3 pilot study showed a
 540 similar treatment effect of overminus in participants with AC/A <2.5 and >=2.5 but had
 541 very few participants with very high AC/A (i.e., larger than 6).

542

543 Subgroup analyses will also be conducted for gender and race/ethnicity in accordance
 544 with NIH guidelines; however, no effect modification is expected for these factors.

545

546 A summary of the subgroups and expected directions of effect modification is shown in
 547 Table 1.

548

549

550

551

552

553

Table 1 – Subgroup Analyses

Factor	Grouping	Expected Direction	Rationale

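### The form of baseline refraction in the 24/36-month refraction model is decided by a check on a different outcome, 12-month distance control, and precision is lost if that check led to categorising

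*SAP*

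**What the plan says.** The extension's objective in Protocol Amendment II is to compare long-term refractive error between the randomised groups. Its analysis paragraph reads: "Spherical equivalent refractive error will be compared between treatment groups using an ANCOVA model that adjusts for baseline spherical equivalent refractive error". It does not mention categorising.

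SAP 5.2.1 adds two rules. First, assumptions for this model are to be checked as in Section 2.1.1, "including linearity of baseline refractive error, normal distribution, and equal variance" across the groups. Second, if baseline refraction was a continuous covariate "in the analysis from Section 2.1, it will be included as a continuous variable in this model" "as well; otherwise, it will be categorized".

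Section 2.1 concerns a different outcome: "The primary analysis will be a two-sided comparison of mean 12-month control of the" distance deviation. Section 2.1.1 settles each covariate's form from that model's own check. A covariate is "included as a continuous variable in the model if the assumptions for linearity are met for" that covariate, and is otherwise categorised. Neither 2.1.1 nor 5.2.1 gives cut-points.

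**The concern.** In the extension model, baseline refraction is the baseline value of the outcome and should be by far its strongest predictor. In the 2.1 model it is one of four adjustment covariates for a control score. A departure from linearity there is no reason to group it here. The reverse error is also possible: a covariate that is linear for control but curved for later refraction would stay linear whatever the 5.2.1 check found.

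The two sentences also fit together poorly. One applies the 2.1.1 approach, in which a model's own check decides the form. The next takes the form from elsewhere and leaves that check without a stated consequence for it. Without cut-points, the categorised branch also leaves the analyst a choice.

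What is at stake is precision, not bias. Under randomisation the treatment estimate is unbiased with either form, but a grouped baseline leaves its within-group variance in the residual. That widens the confidence interval for the extension's main comparison, which was prompted by a myopia safety signal.

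**Working it through.** The documents give no sample size, power or precision target for the 24/36-month comparison, so there is no planned figure to reproduce.

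**Inputs from the documents.** The Protocol Amendment II rationale gives mean 12-month changes of -0.42 D and -0.05 D, a stated difference of 0.39 D, and changes of more than 1.00 D in 29/168 (17.3%) and 3/146 (2.1%). Eligible baseline refraction runs from -6.00 to +1.00 D.

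**Implied SD of 12-month change**, by normal approximation and taking the changes beyond 1.00 D as myopic:
- overminus: (1.00 - 0.42)/z(1 - 29/168) = 0.61 D
- non-overminus: (1.00 - 0.05)/z(1 - 3/146) = 0.47 D

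**Assumptions.** These are not in the documents:
- 150 per arm.
- Progression SD at 24/36 months of 0.5, 0.7 or 1.0 D.
- Follow-up refraction modelled as a level, with slope 1 on baseline.
- Baseline refraction as a gamma distribution shifted to a +1.00 D ceiling, limited to the eligible range in 0.125 D steps. With 17%, 25% or 34% at -0.50 D or below, its SD is 0.64, 0.87 or 1.29 D.

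**Formula.** SE = sqrt[(2/150) × (progression variance + within-category baseline variance)]. With a continuous term the second variance is zero, so at progression SD 1.0 D the SE is sqrt(2/150) = 0.115 D.

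The codings compared are 1 D bands, quintiles, the three groups of SAP 5.5.4 and the two groups of SAP 4.2.1. The last two are tabulation and subgroup codings that the SAP does not assign to this model.

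SE of the treatment difference (D):

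| Baseline SD | Progression SD | Continuous | 1 D bands | Quintiles | Three groups | Two groups |
|---|---|---|---|---|---|---|
| 0.64 | 0.5 | 0.058 | 0.065 | 0.065 | 0.067 | 0.074 |
| 0.64 | 0.7 | 0.081 | 0.086 | 0.086 | 0.087 | 0.093 |
| 0.64 | 1.0 | 0.115 | 0.119 | 0.119 | 0.120 | 0.124 |
| 1.29 | 0.5 | 0.058 | 0.066 | 0.083 | 0.101 | 0.106 |
| 1.29 | 0.7 | 0.081 | 0.087 | 0.100 | 0.115 | 0.120 |
| 1.29 | 1.0 | 0.115 | 0.120 | 0.130 | 0.142 | 0.146 |

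Inflation relative to the continuous term, from unrounded SEs, is 1.03-1.15 (1 D bands), 1.03-1.44 (quintiles), 1.04-1.74 (three groups) and 1.08-1.83 (two groups).

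**Power for 0.39 D**, as Φ(0.39/SE - 1.96). For example, at SE 0.115 this is Φ(3.38 - 1.96) = 92%, and at SE 0.146 it is Φ(2.67 - 1.96) = 76%.

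| Progression SD | Continuous | 1 D bands | Quintiles | Three groups | Two groups |
|---|---|---|---|---|---|
| 0.7 | 99.8% | 99% | 97-99% | 92-99% | 90-99% |
| 1.0 | 92% | 90% | 85-90% | 78-90% | 76-88% |

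At progression SD 0.5 D, where inflation is largest, power stays at about 96% or more under every coding.

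**Cross-check with other baseline shapes** (truncated normal and skewed, SD about 0.7-1.2 D; residual SD 0.6-1.0 D): inflation was 1.03-1.25 for quartiles, 1.05-1.57 for three groups and 1.07-1.61 for two groups. No scenario showed a gain from categorising.

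**Is a linear term safe?** Protocol 4.3.2 reports that "myopic progression was most often observed in overminus group subjects who had spherical equivalent myopia of -0.50 D or greater at baseline". ANCOVA was simulated with that pattern: 1,000 fits per cell, 300 participants, average difference -0.39 D, progression SD 0.5 and 1.0 D, and 0, 0.5 or 1.0 D extra progression in overminus participants at -0.50 D or below. Mean estimates ran from -0.376 to -0.398 D in all cells. With the extra progression, SE relative to the linear term was 1.05-1.17 (1 D bands), 1.04-1.43 (quintiles), 1.03-1.70 (three groups), 1.07-1.78 (two groups) and 1.00 (3-knot spline).

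**The case against.** The strongest reply is that no loss has been shown. Continuous is the form used in 2.1.1 when linearity holds, categorising is the fallback, and nothing in the documents says the fallback was used. The remaining 12-month visits were due by December 2019 and this SAP version is dated February 2021, so its authors may have known which branch applied. That stands, and it makes the point conditional.

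The size rests on assumed SDs, and the largest figures use groupings not written for this model. That also stands. With 1 D bands the loss is at most about 15%, and power below 80% needs the largest progression SD, the widest baseline SD and a two- or three-group coding together.

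The SAP text just before 5.2.1, which may hold the model statement, was not available. If the outcome there were change from baseline, the same slope-1 assumption would give almost no inflation under any coding. However, the Protocol's extension analysis and SAP 4.1.9 both compare refractive error as a level. Other covariates in the 5.2 model cannot be seen either.

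It can also be said that the second sentence is specific and so governs, and that carrying one form across analyses avoids choosing it from the extension data. A continuous term fixed in advance avoids that choice equally well, without borrowing a diagnostic from another endpoint. It does set aside the 2.1.1 principle that each model's check decides the form, which is why a spline sensitivity analysis should accompany it.

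**Conclusion.** The concern holds as a conditional, minor one. SAP 5.2.1 lets a check against distance control force categorisation of the outcome's own baseline in the long-term refraction model, and gives that model's own linearity check no effect on the covariate's form. If that branch applies, the interval for the treatment difference is wider by about 3% to 15% with 1 D bands and by 8% to 83% with two groups, without bias. The practical effect on power is small unless progression SD is near 1.0 D and the coding is coarse. If baseline refraction was continuous in 2.1, there is no loss.

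The size depends on assumed baseline and progression SDs, 150 per arm, a level outcome with slope 1 on baseline, and cut-points the SAP does not give. The mismatch in the rule depends on none of these.

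**What to change.** In SAP 5.2.1, replace the sentence that ties the covariate's form to Section 2.1 with: *Baseline refractive error will be included as a continuous variable.* Add that, if this model's own linearity check shows curvature, the same model with a 3-knot restricted cubic spline (knots at the 10th, 50th and 90th percentiles of baseline refractive error) will be reported as a sensitivity analysis. Section 2.1.1 needs no change.

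The cost is one replaced sentence and one pre-specified sensitivity analysis, with no new data.
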